2.2 Study Flow Chart

The assessment schedule lists all the assessments and when they are performed. All data obtained from these assessments mut be supported in the subject's source documentation. Subjects who prematurely discontinued the study for any reason should be scheduled for a visit as soon as possible. All the assessments listed for the final visit (Visit 4) will be performed. At this final visit, all dispensed investigational treatment should be reconciled, and the adverse events and concomitant medications recorded in the eCRF.

Informed consent must be signed prior to any study-related procedure.

MENARINI	Corporate Medical Department			
Identification Number	Version Number	State	Effective date	
FORM-000050125	2.0, CURRENT	Effective	08, Jan 2021	

	VISIT 1 / WEEK -4	VISIT 2 / WEEK 0± 2 days	VISIT 3 / WEEK 4± 2 days	VISIT 4 / WEEK 8± 2 days
Informed consent submitted	✓	·		
IWRS ^f registration	✓	✓	✓	✓
Inclusion/exclusion criteria	✓			
Medical history	✓			
Prior medications	✓			
Demographic information (for more details see section 8)	*			
Concurrent diseases and medical conditions	✓	✓	✓	✓
Monotherapy of ZOF 30 mg or AML 5 mg dispensing ^a	✓			
Extemporaneous combination of ZOF/AML 30/5 mg dispensing		✓	√b	
Extemporaneous combination of ZOF/AML 30/10 mg dispensing			√c	
Study drug return/accounting (Compliance assessment)		✓	✓	✓
Concomitant medications	✓	✓	✓	✓
Urine Pregnancy test	✓	✓	✓	✓
Physical examination (for more details see section 8)	✓	✓	✓	✓
Vital signs (for more details see section 8)	✓	✓	✓	✓
Laboratory tests ^d	✓			✓
Blood pressure assessment	✓	✓	✓	✓
ECG	✓			✓
AE/SAE assessment ^e	✓	✓	✓	✓

МЕМАЯНИ	Согр	porate Medical Departmo	ent
Identification Number	Version Number	State	Effective date
FORM-000050125	2.0, CURRENT	Effective	08, Jan 2021

Sponsor: Menarini International Operations Luxembourg SA Study Code: MEIN/20/ZoAm-Hyp/001	Protocol Version 1.0 of 1	23/04/2021	
Simily Could highly 20/20/1m Hyp/001			

BP device provided to patientsh	✓			
Patient diary provided to patients ^g	✓	✓	✓	
Patient diary to be returned by patient if used ^g			*	✓
BP device returned to site ⁱ				✓

- a. Patients on ZOF 30 mg or AML 5 mg will continue the same therapy for 4 weeks. Patients on any other ACE-i will be assigned to monotherapy with ZOF 30 mg and the patients on other CCBs (the allowed CCBs are: felodipine, isradipine, lacidipine, lercanidipine, nicardipine, nifedipine, and nisoldipine) will be assigned to monotherapy with AML 5 mg

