- Patients with abnormal renal function (creatinine clearance <30 mL/min) and/or abnormal liver enzyme parameters (alanine aminotransferase [ALT] or aspartate aminotransferase [AST] level of >2.5 × upper limit of normal [ULN] or total bilirubin level >1.5 × ULN).

If a patient has been withdrawn due to an AE, the Investigator must immediately contact the relevant pharmacovigilance contact (see Safety Data Management section). The reason for patient withdrawal must be well-documented in the Electronic Case Report Form (eCRF). The eCRF should capture the date and specific underlying reason for discontinuation of study product or patient discontinuation/withdrawal. Study treatment must be discontinued, and no further assessment conducted, and the data that would have been collected at subsequent visit will be considered missing. Further attempts to contact the patient are not allowed unless safety findings require communication or follow-up. All effort should be made to complete the assessment prior to study withdrawal. A final evaluation at the time of the patient's study withdrawal should be made as detailed in Early termination visit scheduled assessment.

Patients who discontinue from the study early will complete an early termination visit.

MENARINI	Corporate Medical Department		
	** * ** *	G	77.00 dt 1
Identification Number	Version Number	State	Effective date
FORM-000050125	2.0, CURRENT	Effective	08, Jan 2021

Subjects who prematurely withdrawn from study medication or from the study will not be replaced. These subjects will not be considered lost to follow-up.

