#### 5.2.4 Visit Windows

It is expected that all visits should occur according to the protocol schedule. All visit data will be tabulated per the evaluation visit as recorded in the Electronic Case Report Form (eCRF), even if the assessment is outside of the visit window. Early termination visits will be presented in both summary tables and data listings, but unscheduled visits will be presented in the data listings only.

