### 8.3 Clinical Laboratory Evaluations

For laboratory safety continuous variables, values recorded as "<X" or " $\leq$ X" or " $\geq$ Y" or " $\geq$ Y" will be imputed by "X" and "Y" respectively for descriptive statistics. This will be documented in a footnote in all output where such a replacement was performed. Continuous clinical laboratory observed values and change from Baseline (Visit 1) to Visit 4 will be summarized by combined therapy group (ZOF/AML 30/5 mg or ZOF/AML 30/10 mg) and overall for the SAF population.

Each laboratory result will be classified as Normal, Abnormal Not Clinically Significant (NCS), or Abnormal Clinically Significant (CS) at each visit. Shift tables from Baseline (Visit 1) to Visit 4 will be provided for each laboratory parameter, summarized by combined therapy group (ZOF/AML 30/5 mg or ZOF/AML 30/10 mg) and overall for the SAF population. If a patient has a missing lab parameter value at Visit 1 or Visit 4, that patient will be excluded from the shift analysis for that lab parameter but will be included in the corresponding by-patient data listing.

All laboratory parameters will also be presented in by-patient data listings for the SAF population.

Test	Visit	Laboratory Parameters to be Analyzed
		Red blood cell
		White blood cell
		Haemoglobin
		Haematocrit
		Platelets
		Neutrophils
		Lymphocytes
Haematology	Screening (Visit 1) and Visit 4	Monocytes
		Eosinophils
		Basophils
		Neutrophils absolute
		Lymphocytes absolute
		Monocytes absolute
		Eosinophils absolute
		Basophils absolute
		ALT
		Albumin
		Alkaline phosphatase
		AST
		Direct bilirubin
		Total bilirubin
		Total protein
		Creatinine
		Blood urea nitrogen
Serum Chemistry	Screening (Visit 1) and Visit 4	Creatine kinase
		GGT
		Triglycerides
		Cholesterol
		High- and low-density lipoprotein
		Chloride
		eGFR
		Blood glucose
		Potassium
		Uric acid

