### 8.6.2 ECG Variable Analyses

Continuous ECG observed values and change from Baseline (Visit 1) to Visit 4, as well as the number and % of patients in each Rhythm category (Sinusal or Other), will be summarized by combined therapy group (ZOF/AML 30/5 mg or ZOF/AML 30/10 mg) and overall for the SAF population.

ECG Interpretations will be classified as Normal, Abnormal Not Clinically Significant (NCS), or Abnormal Clinically Significant (CS) at each visit. Shift tables from Baseline (Visit 1) to Visit 4 will be provided the EDC Interpretations, summarized by combined therapy group (ZOF/AML 30/5 mg or ZOF/AML 30/10 mg) and overall for the SAF population. If a patient has a missing ECG Interpretation at Visit 1 or Visit 4, that patient will be excluded from the shift analysis but will be included in the corresponding by-patient data listing.

All ECG parameters, including individual results from all 3 measurements at each visit, as well as the final result used in the summary tables, will be presented in a by-patient data listing for the SAF population.

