#### Table 14.3.4.1.1 Summary and Change from Baseline (Visit 1) to Visit 4 for Haematology Parameters (Safety Population)

			ZOF/AML 30/5 mg	ZOF/AML 30/10 mg	All Patients
Parameter (Unit)	Visit [1]	Statistic	(N=xx)	(N=xx)	(N=xx)
xxxxxxx (xxx)	Baseline (Visit 1)	n	xx	xx	ХХ
		Mean (SD)	xx.x (xx.xx)	xx.x (xx.xx)	xx.x (xx.xx)
		Median	xx.x	xx.x	xx.x
		Min, Max	xx, xx	xx, xx	xx, xx
	Visit 4	n	XX	xx	xx
		Mean (SD)	xx.x (xx.xx)	xx.x (xx.xx)	xx.x (xx.xx)
		Median	xx.x	xx.x	xx.x
		Min, Max	xx, xx	xx, xx	xx, xx
	Visit 4 CFB	n	XX	XX	xx
		Mean (SD)	xx.x (xx.xx)	xx.x (xx.xx)	xx.x (xx.xx)
		Median	xx.x	xx.x	xx.x
Repeat for All Parameters		Min, Max	xx, xx	xx, xx	xx, xx

[1] CFB = Change from Baseline. Visit 1 values will serve as Baseline since laboratory parameters are not assessed at Visit 2.
 Source: Listing 16.2.8.1
 Program Name: XXXX.SAS

Date: DDMMMYYYY

- Patients will be classified as either ZOF/AML 30/5 mg or ZOF/AML 30/10 mg such that no patients are counted in both groups. That is, even though patients in the ZOF/AML 30/10 mg group are also exposed to the ZOF/AML 30/5 mg treatment, they will only be included in the ZOF/AML 30/10 mg and All Patients columns, not within the ZOF/AML 30/5 mg column. Same for table in the list below.
- Repeat for the following tables:
  - o 14.3.4.1.2 Summary and Change from Baseline (Visit 1) to Visit 4 for Serum Chemistry Parameters Safety Population
    - Footnote for Source will change to "Source: Listing 16.2.8.2"
    - Source will change to Listing 16.2.8.2

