#### Table 14.3.4.2.1 Shift from Baseline (Visit 1) to Visit 4 for Haematology Parameters (Safety Population)

					Baseline (Visit 1) Value	
Parameter (Unit)	Combined Therapy Group	Visit 4 Value	Statistic	Normal	Abnormal, NCS	Abnormal, CS
xxxxxxx (xxx)	ZOF/AML 30/5 mg (N=xxx)	Normal	n (%)	xx (xx.x)	xx (xx.x)	xx (xx.x)
		Abnormal, NCS	n (%)	xx (xx.x)	xx (xx.x)	xx (xx.x)
		Abnormal, CS	n (%)	xx (xx.x)	xx (xx.x)	xx (xx.x)
	ZOF/AML 30/10 mg (N=xxx)	Normal	n (%)	xx (xx.x)	xx (xx.x)	xx (xx.x)
		Abnormal, NCS	n (%)	xx (xx.x)	xx (xx.x)	xx (xx.x)
		Abnormal, CS	n (%)	xx (xx.x)	xx (xx.x)	xx (xx.x)
	All Patients (N=xxx)	Normal	n (%)	xx (xx.x)	xx (xx.x)	xx (xx.x)
Repeat for All		Abnormal, NCS	n (%)	xx (xx.x)	xx (xx.x)	xx (xx.x)
Parameters		Abnormal, CS	n (%)	xx (xx.x)	xx (xx.x)	xx (xx.x)

Source: Listing 16.2.8.1 Program Name: XXXX.SAS

Date: DDMMMYYYY

- Patients will be classified as either ZOF/AML 30/5 mg or ZOF/AML 30/10 mg such that no patients are counted in both groups. That is, even though patients in the ZOF/AML 30/10 mg group are also exposed to the ZOF/AML 30/5 mg treatment, they will only be included in the ZOF/AML 30/10 mg and All Patients sections, not within the ZOF/AML 30/5 mg section. Same for table in the list below.
- Repeat for the following tables:
  - o 14.3.4.2.2 Shift from Baseline (Visit 1) to Visit 4 for Serum Chemistry Parameters Safety Population
    - Source will change to Listing 16.2.8.2

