#### ZOF/AML 30/5 mg ZOF/AML 30/10 mg All Patients Parameter (Unit) Visit [1] Statistic (N=xx) (N=xx) (N=xx)Baseline (Visit 1) n (%) xx (xx.x) xx (xx.x) xx (xx.x) n (%) xx (xx.x) xx (xx.x) xx (xx.x) Visit 4 n (%) xx (xx.x) xx (xx.x) xx (xx.x) n (%) xx (xx.x) xx (xx.x) xx (xx.x) Baseline (Visit 1) n хх хх хх Mean (SD) xx.x (xx.xx) xx.x (xx.xx) xx.x (xx.xx)

xx.x

xx, xx

хх

xx.x (xx.xx)

xx.x

xx, xx

ΧХ

xx.x (xx.xx)

xx.x

xx, xx

xx.x

xx, xx

ΧХ

xx.x (xx.xx)

xx.x

xx, xx

хх

xx.x (xx.xx)

xx.x

xx, xx

Median

Min, Max

n

Mean (SD)

Median

Min, Max

n

Mean (SD)

Median

Min, Max

Table 14.3.8.1
Summary and Change from Baseline (Visit 1) to Visit 4 for Electrocardiogram (ECG) Parameters
(Safety Population)

[1] CFB: Change from Baseline. Visit 1 values will serve as Baseline since ECG parameters are not assessed at Visit 2. Source: Listing 16.2.11

Visit 4

Visit 4 CFB

Program Name: XXXX.SAS

Date: DDMMMYYYY

xx.x

xx, xx

ΧХ

xx.x (xx.xx)

xx.x

xx, xx

хх

xx.x (xx.xx)

xx.x

xx, xx

Programming Note:

Repeat for All

Parameters

Patients will be classified as either ZOF/AML 30/5 mg or ZOF/AML 30/10 mg such that no patients are counted in both groups. That is, even though patients in the ٠ ZOF/AML 30/10 mg group are also exposed to the ZOF/AML 30/5 mg treatment, they will only be included in the ZOF/AML 30/10 mg and All Patients columns, not within the ZOF/AML 30/5 mg column.

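### Laboratory and ECG values taken at early termination are collected but, as SAP 8.3 and 8.6.2 are written, reach only the listings for patients who stop the combination early

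*SAP*

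**What the plan says.** **Collection.** Protocol Section 10 states: "Patients who discontinue from the study early will complete an early termination visit". Protocol Section 2.2 says of patients who leave prematurely: "All the assessments listed for the final visit (Visit 4) will be performed". The flow chart in that section ticks laboratory tests and ECG at Visit 1 and Visit 4 and at no visit between.

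**General reporting rule.** SAP 5.2.4: "Early termination visits will be presented in both summary tables and data listings, but unscheduled visits will be presented in the data listings only". The same section tabulates data under the visit label recorded in the eCRF.

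**Laboratory and ECG rules.** SAP 8.3 and 8.6.2 summarise continuous change, and tabulate shifts, from Visit 1 (baseline for these data) to Visit 4. For laboratory data: "If a patient has a missing lab parameter value at Visit 1 or Visit 4, that patient will be excluded from the shift analysis". For ECG: "If a patient has a missing ECG Interpretation at Visit 1 or Visit 4, that patient will be excluded from the shift analysis". Both sections keep the excluded patient in the by-patient listing.

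**Shells.** The shift shells follow the same pattern, for example "Table 14.3.4.2.1 Shift from Baseline (Visit 1) to Visit 4 for Haematology Parameters". The continuous shells have rows for Visit 1, Visit 4 and change at Visit 4. Their footnotes explain the choice of baseline: "Visit 1 values will serve as Baseline since laboratory parameters are not assessed at Visit 2" and "Visit 1 values will serve as Baseline since ECG parameters are not assessed at Visit 2".

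**The concern.** The general section promises that early-termination visits will be tabulated. The two sections that need such a rule most leave those visits no cell, and they exclude anyone without a Visit 4 value from the shift.

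Vital signs and physical examination can lose Visit 4 and still show Visit 3. Laboratory tests and ECG cannot, because Visit 4 is their only scheduled post-baseline time point. A patient who starts the combination and then leaves for intolerance, an adverse event, adherence outside 80% to 120%, or Grade 3 blood pressure at Visit 3 therefore counts in the Safety population and in the Visit 1 row, but has no tabulated post-baseline value. The post-baseline, change and shift cells would describe only patients who reached Visit 4, although the protocol plans to collect the missing values. A programmer working from 5.2.4 and one working from 8.3 and 8.6.2 could also produce different tables.

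**Working it through.** The point turns on how the rules fit together. The only arithmetic concerns its size.

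1. **Are the values planned?** Yes. Protocol Section 10 requires the early-termination visit, Section 2.2 gives it the Visit 4 assessments, and the flow chart lists laboratory tests and ECG at Visit 4.

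2. **Could another post-baseline value be tabulated instead?** No. Neither assessment is scheduled at Visit 2 or Visit 3, and SAP 5.2.4 confines unscheduled visits to the listings.

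3. **Do the tables have a place for the values?**

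| Shells | Time points shown | Early-termination row |
|---|---|---|
| 14.3.4.1.1, 14.3.4.1.2 (laboratory summaries) | Visit 1, Visit 4, change at Visit 4 | none |
| 14.3.4.2.1, 14.3.4.2.2 (laboratory shifts) | Visit 1 by Visit 4 | none |
| 14.3.8.1 (ECG summary) | Visit 1, Visit 4, change at Visit 4 (continuous) | none |
| 14.3.8.2 (ECG shift) | Visit 1 by Visit 4 | none |

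That is 4 + 2 = 6 tables, and 0 of 6 have a cell for early termination. They cover 15 + 19 = 34 laboratory rows (SAP 8.3) and 9 ECG parameters (SAP 8.6).

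4. **Does any rule turn early termination into Visit 4?** None is written. SAP 5.2.4 treats early termination as its own kind of visit and relies on the eCRF label. Protocol Section 10 treats data due at later visits as missing. On that text an early leaver's Visit 4 value is missing, and the exclusions in 8.3 and 8.6.2 apply.

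5. **Trace one patient.** A patient on ZOF/AML 30/5 mg has Grade 3 blood pressure at Visit 3, is withdrawn, and has laboratory tests and ECG at early termination. The Visit 1 values enter the baseline row. The early-termination values enter no post-baseline or change cell. The patient is left out of both kinds of shift table, and the pair is visible only in the listings.

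6. **How many patients?** The plan's enrolment figure is 216/(1 − 0.25) = 288, close to the stated 290. The difference, 290 − 216 = 74 (74/290 = 25.5%), does not measure this problem. Protocol Section 5 has 216 patients completing run-in and starting the assessment period, so on that reading the 74 never took the combination. The synopsis includes screening failures in the 25%, and patients with controlled blood pressure at Visit 2 leave by design. Protocol 12.2 can instead be read as a single 25% allowance for the whole study, but it is not split by period. Neither reading gives a number for patients who stop the combination early.

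**The case against.** **The eCRF may already solve it.** Protocol 2.2 calls the discontinuation visit the final visit and gives it Visit 4's content, and the flow chart has no early-termination column. If sites record it as Visit 4, the values enter the Visit 4 cells. This stands as a condition on the point. The eCRF is not available, and SAP 5.2.4 names early termination separately.

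**The shells show scheduled visits only, throughout.** The blood-pressure, vital-sign and physical-examination shells have no early-termination row either, and the laboratory and ECG listing shells name only Visits 1 and 4. So the missing row is not evidence of a decision specific to laboratory and ECG data. The written exclusions in 8.3 and 8.6.2 are specific, and they carry the point.

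**The rules do not strictly contradict.** An early-termination row in the continuous tables, beside a shift restricted to Visit 4, would satisfy both sections. That is fair, but no such row is specified.

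**Collection may be incomplete.** Protocol Section 10 also says that assessments stop at withdrawal and limits further contact. It then asks for a final evaluation on the early-termination schedule, so the values remain planned, though some may be missing.

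**A reader might infer that patients withdrawn for renal or liver abnormalities vanish from the tables.** The schedule does not support that as the main case. A Visit 1 result is a value from before study treatment, and a Visit 4 result is already tabulated. Only an unscheduled sample could trigger a laboratory withdrawal on treatment before Visit 4.

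**Other outputs cover these patients.** Clinically relevant laboratory abnormalities are handled as adverse events (Protocol 9.9). Events leading to discontinuation are tabulated by treatment (SAP 8.2). Disposition Table 14.1.1 has a row for renal or liver abnormality. This stands and limits the severity. What those outputs do not give is the numeric change or the shift category.

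**Conclusion.** The point holds as a minor one. As written, SAP 8.3, 8.6.2 and the six shells leave patients who stop the combination early without any tabulated post-baseline laboratory or ECG value, although SAP 5.2.4 says that early-termination visits are tabulated and the protocol plans the measurements. The loss is confined to descriptive post-baseline, change and shift cells. Efficacy is unaffected.

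The conclusion assumes that the eCRF does not label the early-termination visit as Visit 4 and that early-termination samples and ECGs are in fact obtained. The number of patients is unknown, and 74, or 25%, should not be used for it.

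A reader might also infer that the plan needs separate monotherapy laboratory and ECG tables, because Endpoint 2.5 covers monotherapy and neither assessment is made at Visit 2. The documents do not support that. The absence of Visit 2 samples is a choice about collection, and tables built from early-termination visits would describe only patients who left on monotherapy.

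**What to change.** In SAP 8.3, 8.6.2 and the six shells:

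- For patients who took at least one dose of the combination, define the end-of-treatment value as Visit 4 or, if that is absent, the early-termination value. Use it for the post-baseline, change and shift cells.
- Exclude a patient from a shift table only if Visit 1 or this end-of-treatment value is missing.
- Footnote, per column, how many end-of-treatment values come from early termination.
- Keep values from patients who left on monotherapy alone out of the combination cells. A labelled row or the listing is enough.

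If the eCRF already records early termination as Visit 4, the SAP should say so, and the footnoted count and the separation of monotherapy leavers are still needed.

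The cost is SAP wording and edits to six existing shells, with no added visits, samples or tables. The drawback is that early-termination values follow differing lengths of treatment, so the end-of-treatment column mixes exposure times. The footnote discloses how many values are affected.

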### 8.4 Vital Signs

Vital signs are collected at each study visit and include the following parameters: Systolic Blood Pressure (SBP), Diastolic Blood Pressure (DBP), Heart Rate (HR), and Temperature (temp). Vital sign parameters will be analyzed for the SAF population as follows:

Monotherapy analysis: observed values and change from Screening (Visit 1) to Baseline (Visit 2) will be summarized for each monotherapy group (ZOF 30 mg and AML 5 mg) and for All Patients.

Combined therapy analysis: observed values and change from Baseline (Visit 2) to scheduled postbaseline visits (Visits 3 and 4) will be summarized for each combined therapy group (ZOF/AML 30/5 mg or ZOF/AML 30/10 mg) and for All Patients.

All vital sign parameters will also be presented in a by-patient data listing for the SAF population.

### 8.5 Physical Examination

Physical examination results for each body system will be classified as Normal or Abnormal (CS or NCS) at each visit and will be analyzed as follows:

Monotherapy analysis: shift from Screening (Visit 1) to Baseline (Visit 2) will be summarized (count and percentage) for each monotherapy group (ZOF 30 mg and AML 5 mg) and for All Patients.

Combined therapy analysis: shift from Baseline (Visit 2) to scheduled post-baseline visits (Visits 3 and 4) will be summarized (count and percentage) for each combined therapy group (ZOF/AML 30/5 mg or ZOF/AML 30/10 mg) and for All Patients.

All physical examination details will also be presented in a by-patient data listing for the SAF population.

### 8.6 Electrocardiogram (ECG)

Electrocardiograms (ECGs) are performed in triplicate at Screening (Visit 1) and Visit 4 and include the following parameters: Ventricular Rate (VR), PR Interval, RR Interval, QRS Interval, QT Interval, QTcF, QTcB, Rhythm, and Interpretation.

### 8.6.1 ECG Variable Derivations

For continuous ECG parameters, the mean of all 3 measurements will be presented in the summary tables. For categorical ECG parameters, the most frequently occurring response across all 3 measurements will be presented in the summary tables. If the Interpretation results in a unique response at each of the 3 measurements, then the most severe (Abnormal, Clinically Significant) will be presented in the summary tables.

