FORM-000050125	2.0, CURRENT	Effective	08, Jan 2021

The patient must rest in a supine position for 5 minutes before the ECG is obtained. ECG tracings (paper or electronic) should be reviewed and interpreted by the Investigator or a qualified clinician. ECG parameters including ventricular rate, RR-Interval [ms], PR-Interval [ms], Rhythm (sinusal - other), PR, QRS, QT, QTcF, and QTcB intervals will be recorded.

If QTcF > 450 ms, it should be evaluated and used for clinical decision: another triplicate ECG is indicated and if required should be discussed with the Sponsor and/or medical monitor.

The original ECGs must be appropriately signed, collected and archived at the study site. Printouts and related copies for each ECG will include date, time, initials of the technician/nurse, and initials of the Investigator who reviewed the printout and should be properly archived at site.

Clinically relevant abnormalities should be recorded first on the source documents by the PI and then on the relevant section of the eCRFs.

Laboratory tests

A local laboratory will be used for laboratory evaluation. Clinical laboratory tests (chemistry and haematology) will be conducted at Screening (Visit 1) and Visit 4. Blood and urine samples for pregnancy test will be collected, processed, and analysed locally and in accordance to the research site's SOPs.

The maximum volume of blood to be taken is approximately 40 mL, which will be the total blood collected during the study.

The results should be evaluated for criteria defining AE and reported as such if the criteria are met. In all cases, the investigator must document in the source documents, the clinical considerations (i.e. results were or was not was clinically significant and/or medically relevant) in allowing or disallowing the patient to continue in the study.

To ensure patient safety, the patients will be contacted over phone within 24 hours, in case of any abnormality and clinically relevant laboratory test according to the Investigator's judgement at any visit. The results of laboratory tests will be returned to the Investigator, who is responsible for

MENARINI	Corporate Medical Department		
Identification Number	Version Number	State	Effective date
FORM-000050125	2.0, CURRENT	Effective	08, Jan 2021

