### Table 14.3.8.2 Shift from Baseline (Visit 1) to Visit 4 for ECG Interpretation (Safety Population)

				Baseline (Visit 1) Value	
Combined Therapy Group	Visit 4 Value	Statistic	Normal	Abnormal, NCS	Abnormal, CS
ZOF/AML 30/5 mg (N=xxx)	Normal	n (%)	xx (xx.x)	xx (xx.x)	xx (xx.x)
	Abnormal, NCS	n (%)	xx (xx.x)	xx (xx.x)	xx (xx.x)
	Abnormal, CS	n (%)	xx (xx.x)	xx (xx.x)	xx (xx.x)
ZOF/AML 30/10 mg (N=xxx)	Normal	n (%)	xx (xx.x)	xx (xx.x)	xx (xx.x)
	Abnormal, NCS	n (%)	xx (xx.x)	xx (xx.x)	xx (xx.x)
	Abnormal, CS	n (%)	xx (xx.x)	xx (xx.x)	xx (xx.x)
All Patients (N=xxx)	Normal	n (%)	xx (xx.x)	xx (xx.x)	xx (xx.x)
	Abnormal, NCS	n (%)	xx (xx.x)	xx (xx.x)	xx (xx.x)
	Abnormal, CS	n (%)	xx (xx.x)	xx (xx.x)	xx (xx.x)
	Combined Therapy Group ZOF/AML 30/5 mg (N=xxx) ZOF/AML 30/10 mg (N=xxx) All Patients (N=xxx)	Combined Therapy GroupVisit 4 ValueZOF/AML 30/5 mg (N=xxx)Normal Abnormal, NCS Abnormal, CSZOF/AML 30/10 mg (N=xxx)Normal Abnormal, NCS Abnormal, CSAll Patients (N=xxx)Normal Abnormal, NCS Abnormal, CS	Combined Therapy GroupVisit 4 ValueStatisticZOF/AML 30/5 mg (N=xxx)Normaln (%)Abnormal, NCSn (%)Abnormal, CSn (%)ZOF/AML 30/10 mg (N=xxx)Normaln (%)Abnormal, NCSn (%)Abnormal, CSn (%)Abnormal, CSn (%)All Patients (N=xxx)Normaln (%)Abnormal, NCSn (%)Abnormal, NCSn (%)Abnormal, NCSn (%)Abnormal, NCSn (%)Abnormal, NCSn (%)Abnormal, CSn (%)	Combined Therapy GroupVisit 4 ValueStatisticNormalZOF/AML 30/5 mg (N=xxx)Normaln (%)xx (xx.x)Abnormal, NCSn (%)xx (xx.x)Abnormal, CSn (%)xx (xx.x)ZOF/AML 30/10 mg (N=xxx)Normaln (%)xx (xx.x)Abnormal, CSn (%)xx (xx.x)Abnormal, NCSn (%)xx (xx.x)Abnormal, CSn (%)xx (xx.x)Abnormal, CSn (%)xx (xx.x)All Patients (N=xxx)Normaln (%)xx (xx.x)Abnormal, NCSn (%)xx (xx.x)Abnormal, NCSn (%)xx (xx.x)Abnormal, NCSn (%)xx (xx.x)Abnormal, CSn (%)xx (xx.x)Abnormal, CSn (%)xx (xx.x)Abnormal, CSn (%)xx (xx.x)	Combined Therapy GroupVisit 4 ValueStatisticNormalAbnormal, NCSZOF/AML 30/5 mg (N=xxx)Normaln (%)xx (xx.x)xx (xx.x)Abnormal, NCSn (%)xx (xx.x)xx (xx.x)Abnormal, CSn (%)xx (xx.x)xx (xx.x)ZOF/AML 30/10 mg (N=xxx)Normaln (%)xx (xx.x)Abnormal, CSn (%)xx (xx.x)xx (xx.x)Abnormal, CSn (%)xx (xx.x)xx (xx.x)Abnormal, NCSn (%)xx (xx.x)xx (xx.x)Abnormal, CSn (%)xx (xx.x)xx (xx.x)All Patients (N=xxx)Normaln (%)xx (xx.x)xx (xx.x)Abnormal, NCSn (%)xx (xx.x)xx (xx.x)Abnormal, CSn (%)xx (xx.x)xx (xx.x)Abnormal, NCSn (%)xx (xx.x)xx (xx.x)Abnormal, NCSn (%)xx (xx.x)xx (xx.x)Abnormal, NCSn (%)xx (xx.x)xx (xx.x)

Source: Listing 16.2.11 Program Name: XXXX.SAS

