### Listing 16.2.10 Physical Examination (Safety Population)

Patient ID	Analysis Population [1]	Visit [2]	Date/Time of Assessment	Body System	Result	Clinically Significant	Specify Abnormality
XXXXXX	SAF, EFF, PP	Visit 1, Visit 2, Visit 3, Visit 4	DDMMMYYYY/HH:MM	XXXXXXXX	Normal, Abnormal	Yes, No	XXXXXXX

[1] SAF: Safety Population. EFF: Efficacy Population. PP: Per Protocol Population.

[2] Visit 1 is Week -4. Visit 2 is Week 0. Visit 3 is Week 4. Visit 4 is Week 8. Source: SDTM.XXXX or ADaM.XXXX

Program Name: XXXX.SAS

- Analysis Population column should list *all* populations to which the patient belongs.
- Height (cm), weight (kg), and BMI (kg/m2) are all presented in 16.2.4.1 and thus are not presented here.

Date: DDMMMYYYY

Listing 16.2.11
Electrocardiogram (ECG) Parameters
(Safety Population)

Patient ID	Analysis Population [1]	Visit [2]	ECG Number	Date/Time of Assessment	Parameter (Unit)	Result	Describe CS Interpretation
XXXXXX	SAF, EFF, PP	Visit 1, Visit 4	1, 2, 3	DDMMMYYYY/HH:MM	xxxxxxxx (xxx), Rhythm, Interpretation	xx.x, Sinusal or Other (Specify), Normal, Abnormal NCS, or Abnormal CS	xxxxx

[1] SAF: Safety Population. EFF: Efficacy Population. PP: Per Protocol Population.

[2] Visit 1 is Week -4. Visit 4 is Week 8.

Source: SDTM.XXXX or ADaM.XXXX

Program Name: XXXX.SAS

- Analysis Population column should list *all* populations to which the patient belongs.
- Interpretation and Rhythm will be included as a separate parameter for each ECG number.

Listing 16.2.12.1
Prior and Concomitant Medications
(Safety Population)

Patient ID	Analysis Population [1]	ATC Class Level 1/ Preferred Term [2]	CM #	Start Date / End Date or Ongoing	Indication	Dose (Unit)	Form	Frequency	Route	Prior Med [3,4]	Treatment Given For
XXXXXX	SAF, EFF, PP	xxxxxxx/ xxxxxxxx	ххх	DDMMMYYYY/ DDMMMYYYY or Ongoing	ххх	xxx (xxx)	ххх	ххх	ххх	Yes, No	MH #, AE #, Prophylactically, Other (Specify)

[1] SAF: Safety Population. EFF: Efficacy Population. PP: Per Protocol Population.

[2] WHO Drug Dictionary version YYYYMMM was used to code medication names.

[3] Prior medication is defined as any medication taken within 30 days prior to the start of the study which has a stop date prior to the date of first dose of monotherapy.

[4] Concomitant medication is defined as any medication with a start date on or before the date of *last* dose of study drug and is ongoing or has a stop date on or after date of *first* dose of monotherapy.

Source: SDTM.XXXX or ADaM.XXXX

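### The ECG shift table can show a patient with one clinically significant tracing as Normal or NCS, yet shows a milder mixed set of readings as CS

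*SAP*

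**What the plan says.** SAP 8.6 states: "Electrocardiograms (ECGs) are performed in triplicate at Screening (Visit 1) and Visit 4". SAP 8.6.1 then derives one value per visit. Continuous parameters take the mean of the three. For the rest: "For categorical ECG parameters, the most frequently occurring response across all 3 measurements will be presented in the summary tables". There is one exception, for Interpretation only: "If the Interpretation results in a unique response at each of the 3 measurements, then the most severe (Abnormal, Clinically Significant) will be presented".

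SAP 8.6.2 defines the categories: "ECG Interpretations will be classified as Normal, Abnormal Not Clinically Significant (NCS), or Abnormal Clinically Significant (CS) at each visit". They are summarised in Table 14.3.8.2, "Shift from Baseline (Visit 1) to Visit 4 for ECG Interpretation", with one Interpretation per patient per visit. Rhythm (Sinusal or Other) is summarised in Table 14.3.8.1. Neither shell counts patients with any CS tracing, and neither carries a footnote on how the three readings were combined.

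The individual readings go to a by-patient listing: "All ECG parameters, including individual results from all 3 measurements at each visit, as well as the final result used in the summary tables". The programming note to Listing 16.2.11 adds: "Interpretation and Rhythm will be included as a separate parameter for each ECG number". Separately, Protocol 8.2 says: "Clinically relevant abnormalities should be recorded first on the source documents by the PI and then on the relevant section of the eCRFs".

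**The concern.** SAP 8 names the 12-lead ECG among the safety variables of endpoint 2.5, and Table 14.3.8.2 is the only summary of ECG Interpretation. CS is already a judgement that a finding matters. Under the rule, whether a single CS reading reaches the table depends on whether the other two readings agree with each other, not on the CS reading. A reader who sees a patient in a Normal cell cannot tell from the table that one of the three tracings was read as CS.

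The rule applies at both visits, so the shift can be distorted either way. A CS reading at Visit 4 can be left out, or a CS reading at Visit 1 can be left out so that a finding already present then looks new at Visit 4.

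**Working it through.** The documents state no figure on this point, so there is none to reproduce. The check applies the SAP 8.6.1 rule to every possible set of readings.

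**Inputs.** Three tracings per visit (SAP 8.6); three Interpretation categories (SAP 8.6.2); the mode if at least two agree, otherwise CS (SAP 8.6.1).

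**Sets with exactly one CS reading.**

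| Readings (any order) | Ordered patterns | Shown in Table 14.3.8.2 |
|---|---|---|
| Normal, Normal, CS | 3 | Normal |
| Normal, NCS, CS | 6 | CS |
| NCS, NCS, CS | 3 | NCS |

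Six of these 3 + 6 + 3 = 12 patterns are shown below CS. All ordered triplets number 3³ = 27. Those without CS number 2³ = 8, so 27 − 8 = 19 contain at least one CS. With two or three CS readings the mode is CS, so 6 of 19 is the full count shown below CS.

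**Order of severity.** Start from Normal/NCS/CS, shown as CS. Change the Normal reading to NCS, which is worse. The set becomes NCS/NCS/CS and the displayed value drops from CS to NCS. Worse readings give a milder entry, so the rule is not coherent as a severity summary.

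**Two tracings.** If two are available and they disagree, there is no mode, and the exception is written for three different readings. No value is defined. If a programmer set it to missing, SAP 8.6.2 would drop the patient from the shift table. Fewer than three tracings is a realistic case: Protocol 8.2 describes ECGs at Visits 1 and 4 both as single and as triplicate, and those statements need reconciling.

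**Rhythm.** With two categories, one Other among three tracings is always tabulated as Sinusal in Table 14.3.8.1.

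**Worst of three.** All 12 single-CS patterns would be shown as CS.

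**Illustration of the trade-off, on assumed rates only.** Suppose each tracing is read CS with probability p, otherwise Normal, independently. The mode shows CS with probability 3p²(1−p) + p³; worst-of-three shows it with probability 1 − (1−p)³.

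| Assumed p | Mode | Worst of three |
|---|---|---|
| 0.5 (true intermittent finding) | 50.0% | 87.5% |
| 0.3 (true intermittent finding) | 21.6% | 65.7% |
| 0.05 (over-reading, no true finding) | 0.7% | 14.3% |
| 0.02 (over-reading, no true finding) | 0.1% | 5.9% |

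Tracings from one visit are likely to be correlated, which would make discordant triplets rarer and these gaps smaller. The table shows only that each rule has a cost.

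**The case against.** The case for leaving the rule alone has four parts.

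- **The readings stay visible.** A reader might infer that CS findings are lost. The documents do not support that. Listing 16.2.11 shows each tracing's Interpretation and Rhythm and has a column to describe a CS reading, and Protocol 8.2 sends clinically relevant abnormalities to source and eCRF. This stands: the fault is one of display.
- **The mode is the categorical counterpart of the mean.** Triplicates are replicates of one assessment, and the plan averages replicates elsewhere (blood pressure and continuous ECG parameters). A reader might infer that the rule breaks the SAP's own convention of taking maximum severity and highest relatedness for adverse events (SAP 8.2). That convention covers an event reported several times in a period, so it is an analogy and not a breach. This also stands, but it does not explain why NCS/NCS/CS ranks below Normal/NCS/CS.
- **Worst-of-three is not free.** It raises CS counts. It also applies at Visit 1, where one isolated CS tracing would set baseline to CS, so a sustained CS finding at Visit 4 would no longer appear as a shift from Normal. This stands and shapes the fix.
- **Rhythm has no ranking.** The documents do not say that Other is worse than Sinusal. This stands, so a rule reporting Other whenever any tracing shows it is not justified from the documents.

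**Conclusion.** The point holds as one of inconsistent under-display. As SAP 8.6.1 is written, Table 14.3.8.2 can enter a patient with a CS tracing as Normal or NCS, can rank a worse set of readings below a milder one, and has no defined entry when two available tracings disagree. This follows from the text and rests on no assumption.

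Its reach is limited. Interpretation appears only in Table 14.3.8.2; Table 14.3.8.1 is affected only through Rhythm and cannot show an Interpretation of Normal. A CS reading is outvoted only when the other two agree on a milder one. A reader might take 6 of 19 as the share of CS patients missed, but it gives every pattern equal weight. The documents report no rate of discordant readings, so the number of patients affected cannot be derived. The display is descriptive, and no efficacy result depends on it. It is worth correcting because the table is the sole summary of ECG Interpretation and the change is small.

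**What to change.** 1. Add to Table 14.3.8.2, for each of Visits 1 and 4, the number of patients with at least one CS tracing, by combined therapy group and overall. Include the number with a CS tracing at Visit 4 and none at Visit 1.
2. In SAP 8.6.1, choose one rule for the shift table:
   - the worst available Interpretation at the visit (CS > NCS > Normal); or
   - the mode, with the more severe reading used whenever there is no majority, including when only two tracings are available.
3. Footnote the chosen rule on the table.
4. For Rhythm, keep the stated rule and add to Table 14.3.8.1 the number of patients with any Other tracing.
5. Keep the mean for continuous parameters.

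The first option in step 2 restores a consistent order of severity, at the price of more CS entries and of a baseline set to CS by one isolated tracing at Visit 1. The second avoids those costs but leaves NCS/NCS/CS shown as NCS, so it depends on the counts in step 1 to make such patients visible.

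The cost is a short edit to SAP 8.6.1, a few added rows, a footnote and the matching code. All three readings are already collected and listed.
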